6.3. Measures to Minimize Bias: Randomization and Blinding

This study is a single arm, non-blinded or randomized trial.

6.4. Storage

Bintrafusp alfa drug product should be stored in a refrigerator (2°C to 8°C) until use. Bintrafusp alfa must not be frozen and should be stored in the original packaging.

Additional instructions for the preparation, handling, storage, and disposal of bintrafusp alfa will be provided in the Pharmacy Manual.

6.5. Treatment Compliance

Study treatments will be intravenously administered to participants at the site. Administration will be documented in the source documents and reported in the eCRF.

6.6. Concomitant Medications and Non-Drug Therapies

Participants should receive full supportive care during the study, including transfusion of blood and blood products, and treatment with antibiotics, antiemetics, antidiarrheals, and analgesics, as appropriate. Participants will be instructed to inform the investigator prior to starting any new medications from the time of first dose of study treatment until the end of the study (Final Study Visit). Any concomitant medication(s), including non-prescription medication(s) and herbal product(s), taken during the study will be recorded in the electronic case report form (eCRF). The minimum requirement is that drug name, dose and the dates of administration are to be recorded. Additionally, a complete list of all prior anti-cancer therapies will be recorded in the eCRF.

Palliative radiotherapy may be administered to non-target lesions during the study following discussion with the medical monitor. The indication, dose and dates of administration are to be recorded in the eCRF.

Questions regarding concomitant medications should be directed to the GSK medical monitor for clarification.

If future changes are made to the list of permitted/prohibited medications, formal documentation will be provided by GSK and stored in the study file. Any such changes will be communicated to the investigative sites in the form of a letter.

6.6.1. Prohibited Medicines

Anti-cancer therapy other than bintrafusp alfa (e.g., chemotherapy, radiotherapy, immunotherapy, investigational, etc.) is prohibited except as noted in Section 6.6.

Systemic immunosuppressive drugs are prohibited except as required for the short-term treatment of allergic reactions or immune-related AEs.

Live vaccines should not be administered.

6.7. Dose Modification

Bintrafusp alfa will be administered according to [Table 1](#). Dose modifications are not permitted with the exception of the allowance for bleeding events noted in Section 6.8.5. Dose interruptions are allowed as described [Table 3](#). If there is a dose delay, efficacy assessments must be performed on a calendar schedule and should not be affected by dose interruptions/delays.

6.8. Management of Adverse Events of Interest

Adverse events of interest are serious or nonserious AEs specific to the known mechanism of action of the study intervention that are of clinical interest requiring ongoing monitoring.

6.8.1. Immune-related Adverse Events

Immune-related AEs are specific to immunotherapies and vary by organ system. Immune-related AEs are important identified risks for bintrafusp alfa.

General management by [NCI-CTCAE v5](#) grading, as per ASCO guidelines, is listed below:

- Grade 1: study treatment should be continued with close monitoring, with the exception of some neurologic, hematologic, and cardiac toxicities.
- Grade 2: study treatment may be suspended for most Grade 2 toxicities, with consideration of resuming when symptoms revert to Grade 1 or less. Corticosteroids may be administered (initial dose of 0.5 to 1 mg/kg/d of prednisone or equivalent).

- Grade 3: study treatment is generally suspended and the high-dose corticosteroids (prednisone 1 to 2 mg/kg/d or methylprednisolone 1 to 2 mg/kg/d) treatment should be initiated. Corticosteroids should be tapered over the course of at least 4 to 6 weeks. Some refractory cases may require infliximab or other immunosuppressive therapy.
- Grade 4: in general, permanent discontinuation of study treatment is recommended, with the exception of endocrinopathies that have been controlled by hormone replacement.

Detailed recommendations for irAE management of specific organ systems as per published guidelines are provided in [Appendix 9](#). These recommendations are in accordance with ASCO Clinical Practice Guidelines in collaboration with NCCN guidelines ([Brahmer, 2018](#)).

6.8.2. Potential TGF- β Mediated Dermatologic Adverse Events

Management guidelines for potential TGF- β -mediated dermatologic AEs:

- Discontinuation or interruption of study treatment is generally not required. Continuation of treatment should be evaluated by the investigator.
- Emollients may continue to be used. Diagnostic and treatment plan should be developed in collaboration between investigator and dermatologist. In general, treatment of TGF- β -mediated dermatologic lesions such as hyperkeratosis, KA and cSCC should be based on local guidelines/standard of care. Lesion evaluation should include excision biopsy of one representative lesion to confirm diagnosis.
- Treatment and follow-up for KA and cSCC will depend on number and localization of lesions.
 - For single lesions: Full excision may be recommended.
 - For multiple lesions or location not suitable for full excision other treatment options may be offered by the dermatologist, such as Mohs surgery, cryotherapy, or other standard treatment options depending on the pathology. Use of retinoids if recommended by dermatologist, may be considered after discussion with medical monitor.
- Close clinical follow-up for re-evaluation, resolution, or potential recurrence should be implemented. Spontaneous resolution of KA lesions without surgical intervention has been observed, typically occurring within weeks after discontinuing binrafusp alfa.

The number and localization of lesions, diagnosis (including histopathological diagnosis), treatment, and outcome should be appropriately documented in the eCRF. Consult with study medical monitor as needed for management of TGF- β -mediated dermatologic lesions.

6.8.3. Infusion-related Reactions Including Immediate Hypersensitivity

Infusion-related reactions (IRRs) including immediate hypersensitivity are important identified risks for bintrafusp alfa.

Infusion reactions may vary in manifestation and timing, and signs and symptoms usually develop during or shortly after drug infusion which generally resolves completely within 24 hours of completion of infusion.

Further information regarding mitigation of IRRs are detailed in [Table 2](#).

As a routine precaution, for the first 2 infusions, all participants enrolled in this study must be observed for 2 hours post end of infusion, in an area with resuscitation equipment and emergency agents.

At all times during bintrafusp alfa study treatment, immediate emergency treatment of an IRR or a severe hypersensitivity reaction according to institutional standards must be assured. To treat possible hypersensitivity reactions like anaphylactic reactions, for instance, dexamethasone 10 mg and epinephrine in a 1:1000 dilution or equivalents should always be available along with equipment for assisted ventilation.

Table 3 Treatment Modification for Symptoms of Infusion-Related Reactions

NCI-CTCAE v5 Grade	Treatment Modification
Grade 1 – mild 
 Mild transient reaction; infusion interruption not indicated; intervention not indicated. 	
 Increased monitoring of vital signs as medically indicated, presuming these participants are deemed medically stable.
Grade 2 – moderate 
 Therapy or infusion interruption indicated but if responds promptly to symptomatic treatment (for example, antihistamines, NSAIDs, narcotics, IV fluids); prophylactic medications indicated for ≥24 hours. 	
 Stop binrafusp alfa infusion. 
Increased monitoring of vital signs as medically indicated as participants are deemed medically stable by attending investigator.
 
If symptoms resolve quickly or decreased to Grade 1, resume infusion at 50% of original rate with close monitoring of any worsening otherwise dosing held until resolution of symptoms with mandated premedication for the next schedule.
 
If worsens to Grade 3 or 4, follow treatment modification guidelines accordingly.

Grade 3 or Grade 4 – severe or life-threatening 
 Grade 3: Prolonged (for example, not rapidly responsive to symptomatic medication and/or brief interruption of infusion); recurrence of symptoms following initial improvement; hospitalization indicated for clinical sequelae. Grade 4: Life-threatening consequences; urgent intervention indicated. 	
 Stop the binrafusp alfa infusion immediately and disconnect infusion tubing from the participant with additional appropriate medical measures and close monitoring until deemed medically stable by attending investigator. Hospitalization may be indicated. Participants will be permanently withdrawn immediately from binrafusp alfa treatment and must not receive any further binrafusp alfa treatment

IV = intravenous; NCI-CTCAE v5= National Cancer Institute-Common Terminology Criteria for Adverse Events, version 5; NSAIDs = nonsteroidal anti-inflammatory drugs.

For Grade 3 or 4 infusion-related reactions, binrafusp alfa discontinuation is mandated.

For all types and grades of infusion reactions, details about drug physical constitution, method of preparation and infusion must be recorded.

In the event of a Grade 2 IRR that does not improve or worsens after implementation of the dose modifications indicated in [Table 3](#) (including reducing the infusion rate by 50%), the investigator may consider treatment with corticosteroids and the infusion should be stopped for that day. At the next infusion, the investigator may consider the addition of H2 blocker antihistamines (for example, famotidine or ranitidine), in addition

to premedication, for select participants. However, prophylactic steroids are NOT permitted. At next dose, if the participant has a second IRR Grade ≥ 2 on the slower infusion rate, with the addition of further medication to premedication, the infusion should be stopped, and the participant removed from treatment.

If a severe hypersensitivity reaction occurs, the participant must be treated according to the best available medical practice. Management of hypersensitivity may include:

1. Epinephrine injection and IV dexamethasone
2. Cardiac, blood pressure, heart rate, and oxygen saturation monitoring
3. Intensive care unit transfer if required.

Participants should be instructed to report any delayed reactions to the investigator.

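### Protocol 6.8.3: symptoms that resolve, then return after restart at half rate, meet Table 3's Grade 3 criterion (permanent withdrawal), but the paragraph below can be read to allow a next infusion

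*Protocol*

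**What the plan says.** All the relevant text is in Protocol Section 6.8.3.

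- **Grade 2 definition (Table 3):** "Therapy or infusion interruption indicated but if responds promptly to symptomatic treatment".
- **Grade 2 action, restart:** the infusion is stopped, then "If symptoms resolve quickly or decreased to Grade 1, resume infusion at 50% of original rate with close monitoring of any worsening". If that condition is not met, dosing is held until symptoms resolve, and premedication is required next time.
- **Grade 2 action, escalation:** "If worsens to Grade 3 or 4, follow treatment modification guidelines accordingly".
- **Grade 3 definition:** "Grade 3: Prolonged (for example, not rapidly responsive to symptomatic medication and/or brief interruption of infusion); recurrence of symptoms following initial improvement". Hospitalization for clinical sequelae is a further criterion.
- **Grade 3 or 4 action:** "Participants will be permanently withdrawn immediately from binrafusp alfa treatment and must not receive any further binrafusp alfa treatment". The text directly under the table repeats this: "For Grade 3 or 4 infusion-related reactions, binrafusp alfa discontinuation is mandated".
- **Later paragraph:** "In the event of a Grade 2 IRR that does not improve or worsens after implementation of the dose modifications indicated in" Table 3, with the 50% rate reduction named in parentheses. Corticosteroids may be considered, and "the infusion should be stopped for that day. At the next infusion, the investigator may consider the addition of H2 blocker antihistamines". The participant is removed only if a second reaction of Grade 2 or higher occurs at that next dose.

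**The concern.** A restart at half rate always follows an improvement, because Table 3 allows it on no other condition. If the symptoms had gone and then come back at half rate, the Grade 3 wording applies and treatment ends. The later paragraph describes a Grade 2 reaction that gets worse after the half-rate step, and a site could readily place the same event there. It would then stop for the day and plan the next dose.

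The risk is re-exposure. The protocol classes infusion reactions, including immediate hypersensitivity, as an important identified risk, and a site following the paragraph could re-dose someone whom Table 3 bars from further drug. The question is still live for anyone on treatment. Section 6.10 makes not meeting a discontinuation criterion one condition for continued access after the data cut-off, so it must be clear whether this event is such a criterion.

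**Working it through.** The plan gives no figure to reproduce. The check traces one event through both texts and then tests the neighbouring cases.

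**Trace of the central case**

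1. A Grade 2 reaction occurs and the infusion is stopped (Table 3, Grade 2 row).
2. Symptoms resolve quickly. That is an improvement, and it opens the half-rate restart (same row).
3. Symptoms return at half rate. Under the Grade 3 definition, return after initial improvement is a criterion of its own, separated from the others by semicolons. The Grade 2 row's escalation line then leads to the Grade 3 or 4 action: 0 further infusions.
4. Under the later paragraph, the same event can be taken as a Grade 2 reaction that worsened after the rate was halved: stop for the day, then at least 1 further planned infusion.

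**Neighbouring cases**

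| Course of the reaction | Table 3 | Paragraph under Table 3 | Conflict? |
|---|---|---|---|
| Resolves, restarted at half rate, returns | Grade 3, withdraw | Can be read as Grade 2 that worsens; next infusion planned | Yes |
| Falls to Grade 1, restarted, Grade 1 intensifies | Unclear whether this counts as recurrence | Grade 2 that worsens, if it reaches Grade 2 | Ambiguous |
| Falls to Grade 1, restarted, Grade 1 merely persists | Not a recurrence | Reaction that does not improve | No |
| Not restarted, dosing held | Grade 2 row: hold, premedicate next time | Stop for the day, premedicate next time | No |

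The last row assumes that the reaction is not prolonged. If it is, Table 3 already makes it Grade 3.

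**Does another section rank the two texts?**

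- 6.7 refers dose interruptions to Table 3 but does not place the table above the paragraph.
- 7.1 sends the reader back to 6.8 for the adverse events of interest that require withdrawal.
- 7.1.4 says that 6.8 overrides its own general stopping rules. Both texts are in 6.8, so this does not choose between them.
- 8 asks that immediate safety concerns be discussed with the sponsor. This is a safeguard, not a precedence rule.

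**Size**

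The difference is 0 versus at least 1 further planned infusion per affected participant. Section 1 reports 25 treated, so the number affected lies between 0 and 25. The documents do not narrow that range.

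**The case against.** The best answer is that a site grades first and acts second. The paragraph is limited to Grade 2 reactions. The mandate for Grades 3 and 4 stands shortly before it, and the Grade 2 row passes anything that reaches Grade 3 to withdrawal. On that reading a recurrence is graded 3 and never enters the paragraph. The reading is defensible, and it is why the paragraph should be described as capable of being misread rather than as ordering a re-dose. It does not remove the problem. The paragraph expressly includes the half-rate step, that step always follows an improvement, and the paragraph does not say that a return at that point has left Grade 2.

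Three other objections stand in whole or in part.

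- **Worsening is not the same as recurrence.** A reader might infer that any worsening at half rate is Grade 3. The documents do not support that. Table 3 permits restart with Grade 1 symptoms still present, asks for monitoring of worsening, and escalates only at Grade 3 or 4. Residual symptoms that intensify have not clearly recurred.
- **The paragraph also has uncontested content.** It covers Table 3's modifications generally, and for a reaction that was never restarted it agrees with the Grade 2 row.
- **Safeguards exist.** The infusion stops that day, emergency treatment must be available, the investigator may discontinue for safety at any time (7.1), and a second reaction at the next dose leads to removal.

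**Conclusion.** The point holds in a narrow form. For symptoms that resolve, are followed by a half-rate restart and then return, Table 3 requires permanent withdrawal, while the paragraph beneath it can be read to plan another infusion. Nothing elsewhere in the protocol decides between them. This rests on reading Table 3's recurrence criterion as printed, as sufficient by itself for Grade 3.

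A reader might want to express the harm as all the infusions left on a two-year, every-two-weeks schedule. The documents do not support that measure. Enrollment has ceased and the 25 reported participants had already been dosed, so a reaction at a first dose can no longer be affected by new wording. Infusions given after a tolerated next dose are also not a count of harm. The supported contrast remains the single planned re-dose, in participants still on treatment. It may apply to nobody: Table 2 of Section 2.2.5 describes earlier infusion reactions as mild to moderate, and Section 1 reports no new safety signals.

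The definition and analysis of ORR are unaffected. This is a dosing-safety ambiguity with small exposure and a cheap remedy, worth correcting while anyone remains on drug.

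**What to change.** Add one sentence to the paragraph under Table 3. It should say that symptoms which return after resolution and a restart at 50% rate are Grade 3 under Table 3 and lead to permanent withdrawal, and that the next-dose pathway applies only to reactions that have not met any Grade 3 criterion. Tell sites by letter, for participants still on treatment.

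Table 3 and the SAP need no change. The cost is one sentence and one letter. The downside is that a participant may be withdrawn sooner than under the looser reading, which the existing mandate already requires.

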6.8.4. Treatment-related Anemia

A thorough investigation of new anemia cases of unspecified etiology is expected. For new anemia events assessed as treatment-related, items queried may include, but are not limited to, detailed relevant past medical and treatment history, bruising tendency, history of blood transfusions and/or dependency, and a request for an updated eCRF including details such as concomitant medications, all laboratory data, updated dosing information and recent tumor evaluation scans.

General guidance for anemia management and evaluation:

1. Participants must enter the study with hemoglobin values at least 9 g/dL; routine blood test parameters are specified in [Appendix 2](#).
2. Transfusion should be performed at the discretion of the investigator.
3. Relevant hematologic testing for treatment-related anemias should be done prior to blood transfusion, if clinically feasible. Guidance for evaluation of suspected treatment-related anemias is provided in [Table 4](#).
4. Discuss further management with medical monitor for clinically significant treatment-related anemias.

Guidance for evaluation of suspected treatment-related anemias is provided in [Table 4](#).

Table 4 Evaluation Guidance of Suspected Treatment-related Anemia Adverse Events

Baseline anemia evaluation (prior to transfusion, if feasible)	
Hb and CBC with differential (eg, MCV, RDW, ANC, hematocrit, reticulocytes counts)	
Peripheral blood smear for cell morphological assessment	
Complete metabolic panel including liver panel-LFTs, bilirubin, LDH, renal function, and serum folate, B12 values and other chemistries	
Coagulation factors (PT, PTT, INR)	
Urinalysis including culture	
Iron panel (TIBC, ferritin, iron)	
TSH/hormonal panel	
Fecal-occult blood testing	
Erythropoietin	
Haptoglobin	
Further recommendation based on suspected etiology (in addition to Baseline anemia testing)	
Unknown etiology, suspect possible hemolysis	Coombs test, fibrinogen, d-dimer. Consider hematology consultation. Consider blood transfusion at clinical discretion.
Unknown etiology, suspect possible bleeding	Consider blood transfusion at clinical discretion. Consider surgical/interventional radiology consultation. Consider imaging, as clinically indicated (eg, FAST scan, CT scan, MRI, angiography). Consider endoscopy (upper/lower)
Unknown etiology despite above work-up	Hematology consultation Consider bone marrow aspiration/morphologic evaluation

ANC = absolute neutrophil count; CBC = complete blood count; CT = computed tomography; FAST = focused assessment with sonography for trauma; Hb = hemoglobin; INR = international normalized ratio; LDH = lactate dehydrogenase; LFT = liver function test; MCV = mean corpuscular volume; MRI = magnetic resonance imaging; PT = prothrombin time; PTT = partial thromboplastin time; RDW = red cell distribution width; TIBC = total iron-binding capacity; TSH = thyroid-stimulating hormone.

6.8.5. Additional Risks

6.8.5.1. Bleeding Events

Bleeding events are a potential risk for bintrafusp alfa (refer to IB).

For all participants:

For Grade ≥ 2 tumor bleeding, study treatment must be held until the event recovers to Grade ≤ 1 . If a Grade ≥ 3 tumor bleeding event has been observed, regardless of causality with the study intervention, upon resumption of the study intervention the bintrafusp alfa dose should be reduced to 600 mg Q2W. Once there is stable resolution and no recurrence of bleeding on the reduced dose, the investigator is encouraged to communicate with the medical monitor regarding a potential dose re-escalation after careful benefit-risk assessment. Treatment should be permanently discontinued if the investigator considers the participant to be at risk for additional severe bleeding. In case of a rapid decrease of hemoglobin (Hgb), see [Table A8](#) (Management of Hematologic irAEs in Patients Treated with ICPis) in Section [10.9](#).

If a Grade ≥ 3 non-tumor bleeding event is observed, study treatment must be permanently discontinued unless an alternative explanation can be identified (such as concomitant use of antithrombotic agents, traumatic event, etc.). In case of alternative explanations for the Grade ≥ 3 bleeding event, study treatment should be held until the event recovers to Grade ≤ 1 . If a Grade ≥ 3 bleeding event is observed, regardless of causality with the study intervention, upon resumption of study intervention, the bintrafusp alfa dose should be reduced to 600 mg Q2W. Once a Hgb decrease recovers to Grade ≤ 1 or there is stable resolution and no recurrence of bleeding on the reduced dose, the investigator is encouraged to communicate with the medical monitor regarding a potential dose re-escalation after careful benefit-risk assessment. The dose of bintrafusp alfa may be re-escalated to full dose (1200 mg Q2W) once Hgb is stabilized without further need for blood transfusion in the subsequent cycles. The timing of re-escalation will be determined on a case-by-case basis. See Section 6.8.4 regarding the stabilization of anemia.

For Grade 4 non-tumor bleeding, treatment must be permanently discontinued if no alternative explanation is identified. In case of rapid decrease of Hgb, such as a decrease greater than 2.0 g/dL across a 2-week period, withhold the subsequent cycles of study intervention until Hgb is stabilized and do a thorough assessment of bleeding (for example, upper and lower gastrointestinal [GI] endoscopy, contrast-enhanced CT scan, etc.). If Grade ≥ 1 bleeding is observed or suspected, withhold the bintrafusp alfa until the bleeding is resolved/controlled and resume the dose of bintrafusp alfa, decreased to 600 mg Q2W. The dose of bintrafusp alfa may be re-escalated to full dose (1200 mg Q2W) once Hgb is stabilized to Grade 1 or baseline without further need for blood transfusion in the subsequent cycles; the investigator is encouraged to communicate with the medical monitor to re-escalate the dose. The timing of re-escalation will be determined on a case-by-case basis. See Section 6.8.4 regarding stabilization of anemia.

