7.1.4. Adverse Drug Reaction Stopping Criteria

Adverse drug reactions are defined in this study as any AEs related to study intervention assessed by the investigator and/or sponsor.

Management guidelines for AEs of Interest (Immune-related AEs, TGF- β -mediated dermatologic AEs, Infusion-related reactions, and treatment-related anemia) as described in Section [6.8](#) supersede the general guidelines below.

Adverse Drug Reactions (ADRs) requiring discontinuation of study treatment include:

- Any Grade 4 ADRs.
- Persistent Grade 3 non-hematologic ADRs that do not recover to Grade 0 or 1 within 6 weeks after dose of treatment Recurrent Grade 3 ADRs (after recovery to Grade 0 or 1) that last more than 72 hours, with optimal medical management, also require discontinuation.
- Any ADR requiring treatment with corticosteroids beyond 12 weeks at doses greater than 10 mg prednisone (or equivalent) per day.

Exceptions to the criteria for discontinuation:

- Fatigue.
- Isolated laboratory values out of normal range that do not have any clinical correlation.
- Endocrinopathies controlled with hormone replacement therapy.
- Tumor flare phenomenon defined as local pain, irritation, or rash localized at sites of known or suspected tumor.
- Keratoacanthomas and/or cSCC (see Section [6.8.2](#)).

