#### **14.1.6. AEs OF SPECIAL INTEREST**

AEs of Special Interest (AESI) will be identified by a standardized list of MedDRA preferred terms to be updated on an ongoing basis during the study. The AESIs defined for this study are:

- Infusion-related Reactions
- Immune-related AEs
- TGF- $\beta$  inhibition mediated skin events including skin lesions

Document: [\\quintiles.net\\Enterprise\\Apps\\sasdata\\SAS\\sas\\GSK\\GSK4045154\\PZAA7715\\Biostatistics\\Documentation\\SAP\\GSK\\_213152\\_PZAA7715\\_SAP\\_Final\\_v1.0\\_07SEP2022](\\quintiles.net\\Enterprise\\Apps\\sasdata\\SAS\\sas\\GSK\\GSK4045154\\PZAA7715\\Biostatistics\\Documentation\\SAP\\GSK_213152_PZAA7715_SAP_Final_v1.0_07SEP2022)

Author: PPD Version Number: 1.0  
Version Date: 07SEP2022

Template No.: CS\_TP\_BS016 Revision 6

Reference: CS\_WI\_BS005

Effective Date: 02Dec2019

- Treatment related Anemia
- Bleeding events
- Wound healing delay
- Secondary malignancies
- Embryofetal toxicities.

Further details of the derivation of the AESI can be found in Appendix 3.

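### Protocol 7.1.4 and 6.8.5.1 do not settle which passage governs a treatment-related Grade 4 tumor bleed

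*Protocol*

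**What the plan says.** Protocol 7.1.4 gives this definition: "Adverse drug reactions are defined in this study as any AEs related to study intervention assessed by the investigator and/or sponsor". Its list of events that require discontinuation starts with "Any Grade 4 ADRs". Before that list stands a precedence clause. It refers to the guidelines for AEs of interest and names, in parentheses, immune-related AEs and TGF-β-mediated dermatologic AEs, closing with "Infusion-related reactions, and treatment-related anemia) as described in Section" 6.8. Those guidelines "supersede the general guidelines below". A further list, introduced by "Exceptions to the criteria for discontinuation", has five entries: fatigue, isolated laboratory values, endocrinopathies controlled by hormone replacement, tumor flare, and keratoacanthoma or cSCC.

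Protocol 6.8.5.1 treats bleeding in three parts.

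- **Tumor bleeding.** From Grade 2 upward, treatment is held until Grade 1 or lower. From Grade 3 upward the text adds: "regardless of causality with the study intervention, upon resumption of the study intervention the bintrafusp alfa dose should be reduced to 600 mg Q2W". Treatment ends permanently if the investigator sees a risk of further severe bleeding.
- **Non-tumor bleeding.** From Grade 3 upward, treatment ends permanently unless there is another explanation. A separate Grade 4 sentence repeats this for non-tumor bleeding only.
- **Rapid hemoglobin fall.** Treatment is withheld. If bleeding of any grade is seen or suspected, it is resumed at the reduced dose once the bleeding is controlled.

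**The concern.** Two stopping rules reach the same event and can lead to different outcomes. A site that works from 6.8.5.1 could re-dose after a life-threatening bleed judged related to treatment. A site that works from 7.1.4 would conclude that treatment has to end. Resuming would be a protocol deviation on one reading and not on the other.

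The question also outlasts enrollment. Sections 6.10 and 8.2 allow treatment after the data cut-off only for participants who meet no discontinuation criterion of the protocol. For this event, whether such a criterion is met is what the text leaves open.

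**Working it through.** The check is textual; no arithmetic applies beyond counting entries.

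**Step 1. Does 7.1.4 reach the event?** A related bleed is an ADR by definition, and Grade 4 is on the discontinuation list. Yes.

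**Step 2. Does the tumor-bleeding text of 6.8.5.1 reach it?** Grade 4 lies within Grade 3 or higher, and the text applies whatever the causality, so related events are included. Yes.

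**Step 3. Does 7.1.4 hand the event over?** The four named groups match 6.8.1, 6.8.2, 6.8.3 and 6.8.4 one for one (4 of 4). Section 6.8.5 has three subsections (bleeding, wound healing, embryofetal toxicity), and none is named (0 of 3). Bleeding is none of the five exceptions (0 of 5). The named anemia group does not bring it in, because 6.8.4 describes work-up and contains no rule on stopping or resuming.

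**Step 4. Does 6.8.5.1 claim precedence?** No. Its Grade 4 sentence is confined to non-tumor bleeding. Its pointer to Table A8 concerns a rapid hemoglobin fall, and none of that table's seven headings (8.1 to 8.7) is tumor bleeding.

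**Step 5. Does another passage decide?** Four lean towards 6.8.5.1:

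- It sits inside Section 6.8, titled "Management of Adverse Events of Interest".
- Section 7.1 refers to Section 6.8 as a whole for AEs that require discontinuation.
- Table 2 sends the reader to 6.8.5.1 for bleeding.
- The list that SAP 14.1.6 opens with "The AESIs defined for this study are" includes bleeding events.

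None of the four says which section prevails.

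**Step 6. How wide is the gap?**

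| Grade 4 bleed | 7.1.4 | 6.8.5.1 | Result |
|---|---|---|---|
| Tumor, unrelated | Not an ADR | Hold; stop or resume by judgment | One passage applies |
| Tumor, related | Stop, if the four groups are a closed list | Hold; stop or resume by judgment | Not settled |
| Non-tumor, related, no other explanation | Stop | Stop | Same outcome |
| Non-tumor, other explanation | Applies only if still assessed as related | Hold; resumption possible | Open only if still assessed as related |

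The clear open case is the second row.

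**Step 7. The hemoglobin text.** It follows the non-tumor sentence, but its wording is not limited to non-tumor bleeding. It is also phrased more as an instruction to resume than the tumor-bleeding paragraph is. A related Grade 4 tumor bleed with a rapid hemoglobin fall could therefore fall under it as well.

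**The case against.** The strongest reply is that the passages can be obeyed together. The tumor-bleeding paragraph sets a dose for the case in which treatment resumes; it does not order resumption. Section 7.1.4 can then decide whether treatment may resume at all. Its parenthesis carries no sign that the groups are only examples, whereas Protocol 9.4.5 marks its examples as such. Stopping breaches neither the tumor-bleeding paragraph nor 7.1.4, so a compliant path exists. All of this stands. A reader might infer that the protocol flatly contradicts itself or requires re-dosing after a related Grade 4 tumor bleed. The tumor-bleeding text does not support that.

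The opposite reply is that the specific bleeding guidance naturally prevails over a general rule. The passages in Step 5 give this some force. But 7.1.4 has its own precedence clause, and that clause lists its groups without bleeding.

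A third reply is that no case would be handled by the investigator alone. Section 8 sends immediate safety concerns to the sponsor, and 8.5.1 requires SAE reports within 24 hours. Section 8.6 requires a discussion with the medical monitor once three or more consecutive doses are held. Sections 6.10 and 8.2 require the medical monitor's agreement after the cut-off. These provisions make a split between sites less likely, but they give the sponsor no written order of precedence to apply. Section 8 also bars waivers, so if 7.1.4 governs, consultation could not permit resumption.

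**Conclusion.** The point holds as an unresolved question of precedence, and it is minor. It concerns one narrow event: Grade 4, tumor bleeding, assessed as related. The primary response analysis is unaffected. The protocol reports 25 participants treated at Amendment 02. The documents give neither a rate for this event nor the number still on treatment, so no expected count can be stated. The conclusion assumes only that a related bleed is an ADR, as 7.1.4 defines it.

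Two further inferences are tempting and are not supported.

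- **That Amendment 02 overlooked 7.1.4.** The visible change log has entries for 6.7 and 8.6 and none for 7.1.4. The log is partly redacted and records only changes, so its silence proves nothing.
- **That SAP 14.1.2 is deficient because it has no row for dose reduction.** Its infusion-rate rows already cover a form of modification. Reporting is abbreviated, and reductions would still show in the exposure summaries and listings. The SAP cites an eCRF version of 10-Jun-2020, before Amendment 02 (03-Mar-2022), so the documents do not show whether a dose-reduction code exists. An extra row is a matter of presentation, and no change is asked for.

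**What to change.** Reconcile 7.1.4 with 6.8.5.1 by stating in 7.1.4 whether bleeding events under 6.8.5.1 are among the Section 6.8 guidelines that override it. A related Grade 4 tumor bleed then has one governing passage, and the condition for continued treatment in 6.10 and 8.2 becomes determinate. In the same change, say whether the rapid-hemoglobin-fall text of 6.8.5.1 applies to tumor bleeding and how it ranks against 7.1.4. Which clinical rule results is for the sponsor to decide.

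The cost is a sentence or two in a clarification letter or amendment. No data collection, analysis or table changes.
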